## **Adverse events of study treatment:**

We hypothesize that participants randomized to convalescent plasma will not have any increased risk to standard transfusions. Preliminary data from the expanded access protocol for treatment of COVID-19 by convalescent plasma among those with severe disease, suggests that the treatment is safe with low number of adverse events [Joyner et al, J Clin Invest. 2020].

Adverse event data will be collected continuously throughout the trial and analyzed by treatment group at each interim analysis. We will also compare the rates of all serious adverse events (as

specified by the Health and Human Services definition) using cumulative incidence. The primary safety endpoints are i) the cumulative incidence of treatment-related serious adverse events categorized separately as either severe infusion reactions or Acute Respiratory Distress Syndrome (ARDS) during the study period and ii) cumulative incidence of treatment-related grade 3 and 4 adverse events during the study period.

Data collection for adverse events will be done via a combination of specific questions for anticipated effects and spontaneous participant report. We will present overall number of AEs and SAEs by treatment group and where differences exist, we will present those by organ system. As these are descriptive safety analyses no correction for multiplicity will be undertaken.

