Primary Efficacy Objective: Evaluate the efficacy of treatment at Day 28 following high-titer Anti- SARS-CoV-2 plasma versus control (SARS-CoV-2 non-immune plasma) in subjects exposed to COVID-19 at day 28.

Primary Endpoint: Cumulative incidence of development of COVID-19 disease (symptoms compatible with infection and/or + molecular testing) regardless of disease severity.

Primary Safety Objective: Evaluate the safety of treatment with high-titer Anti- SARS-CoV-2 plasma versus control (SARS-CoV-2 non-immune plasma) in subjects exposed to COVID-19

Primary Safety Endpoints:

1. Cumulative incidence of serious adverse events categorized separately as either severe infusion reactions and ARDS during the study period
2. Cumulative incidence of grade 3 and 4 adverse events during the study period

Secondary Objectives:

1. Cumulative incidence of disease severity between the anti-SARS-CoV-2 convalescent plasma and control groups after individuals develop SARS-CoV-2 infection. Severity of disease will be measured using a clinical event scale of disease severity (evaluated up to Day 28):
 1. Death
 2. Requiring mechanical ventilation and/or in ICU
 3. non-ICU hospitalization, requiring supplemental oxygen;
 4. non-ICU hospitalization, not requiring supplemental oxygen;
 5. a stay of >24 hours for observation in an ED, field hospital, or other healthcare unit*
 6. any receipt of O2 for >24 hours, outside of hospital*
 7. Not hospitalized, but with clinical and laboratory evidence² of COVID-19 infection

² Positive molecular testing for SARS-CoV-2

*with surge of infections in December 2020 and hospitals becoming more full, these two were put into the clinical events scale as hospitalization equivalents

Other Objectives:

1. Compare the anti-SARS-CoV-2 convalescent plasma and control (SARS-CoV-2 non-immune plasma) groups' anti-SARS-CoV-2 titers at days -1 to 0, 1, 7, 14 and 90.
2. Compare the rates and duration of SARS-CoV-2 molecular testing positivity amongst the anti-SARS-CoV-2 convalescent plasma and control (SARS-CoV-2 non-immune plasma) groups at days 1, 7, 14 and 28
3. Compare the levels of SARS-CoV-2 RNA amongst the anti-SARS-CoV-2 convalescent plasma and control (SARS-CoV-2 non-immune plasma) groups at days -1 to 0, 1, 7, 14 and 28

Table of Contents

1. PROTOCOL SUMMARY:	1
1.1. STUDY POPULATION:	5
1.1.1. Inclusion Criteria for Enrollment:	5
1.1.2. Exclusion Criteria	5
2. LIST OF ABBREVIATIONS:	5
3. BACKGROUND AND SCIENTIFIC RATIONALE	6

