5.3. Endpoints

Primary Efficacy Endpoint:

28 day incidence of COVID-19 infection with both clinical and laboratory evidence.

Primary Safety Endpoints:

1. Cumulative incidence of serious adverse events categorized separately as either severe infusion reactions and ARDS during the study period
2. Cumulative incidence of grade 3 and 4 adverse events during the study period

Secondary Endpoints

1. 28 day incidence of severe COVID-19 infection defined by death or initiation of mechanical ventilation.
2. Anti-SARS-CoV-2 titers at days -1 to 0, 1, 7, 14, and 90.
3. Rates and duration of SARS-CoV-2 molecular testing positivity at days 1, 7, 14, and 28.

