7. RISKS AND BENEFITS

Potential Benefits of treatment

The potential benefits of antiviral treatment with anti-SARS CoV-2 plasma in patients at high risk for developing COVID-19 due to a close contact with another individual with COVID-19 are unknown. However, it is anticipated that treatment will decrease the risk of developing symptomatic disease and decrease the severity of illness should it develop.

Potential benefits of clinical monitoring and virologic testing

Subjects enrolled in the study will undergo close clinical and virologic monitoring that could facilitate earlier diagnosis of development of COVID-19 with associated benefit to the individual, their family and the community at large.

Potential risks

1. Risks of plasma: Fever, chills, rash, headache, serious allergic reactions, TRALI, TACO, transmission of infectious agents
2. Risks of phlebotomy: local discomfort, bruising, hematoma, bleeding, fainting,
3. Total blood draws will not exceed 500 mL
4. Risks of oropharyngeal and throat swab: local discomfort, vomiting

Alternatives

The alternative to participation in this study is routine care and monitoring following close contact with an individual with COVID-19

Safety measures

1. Safety Evaluations will assess for the safety of high titer anti-SARS-CoV-2 plasma and determine if it is higher, lower or the same as SARS-CoV-2 non-immune plasma
2. Clinical evaluations: In-person vital signs and symptom screen on days 0,1,7,14 and remote (phone call) symptom screens on days ,3 and 60
3. Laboratory evaluations

4. Safety laboratory tests (ABO typing, pregnancy testing, CBC and comprehensive metabolic panel) will be performed at the local CLIA-certified clinical laboratory on days -1 to 0, 1, 7 and 14

Event (AE)

Any untoward medical occurrence in a clinical investigation subject who has received a study intervention and that does not necessarily have to have a causal relationship with the study product. An AE can, therefore, be any unfavorable and unintended sign (including an abnormal laboratory finding, for example), symptom, or disease temporally associated with the use of the study product, whether or not considered related to the study product.

Serious Adverse Event (SAE)

An SAE is any adverse event that results in any of the following outcomes:

1. Death;
2. Life-threatening (immediate risk of death);
3. Inpatient hospitalization or prolongation of existing hospitalization;
4. Persistent or significant disability or incapacity;

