7.1. Reporting Interval

All AEs and SAEs will be documented from the first administration of study product All AEs and SAEs will be followed until resolution even if this extends beyond the study-reporting period. Resolution of an adverse event is defined as the return to pre-treatment status or stabilization of the condition with the expectation that it will remain chronic.

Reporting should also occur at any time after completion of the study, if the investigator becomes aware of a SAE that is suspected to be related to study product

Investigator's Assessment of Adverse Events

The determination of seriousness, severity, and causality will be made by an on-site investigator who is qualified (licensed) to diagnose adverse event information, provide a medical evaluation of adverse events, and classify adverse events based upon medical judgment. This includes but is not limited to physicians, physician assistants, and nurse practitioners.

Laboratory abnormalities will be reported as AEs if they are considered clinically significant by the investigator.

Assessment of Seriousness

- I. Event seriousness will be determined according to the protocol definition of an SAE
- II. Assessment of Severity

Event severity will be assigned according to the MedDRA parameters in the EDC, which correspond to the following definitions:

- 1 = Mild: Transient or mild discomfort (<48 hours); no medical intervention/therapy required.)
- 2 = Moderate: Mild to moderate limitation in activity-some assistance may be needed; no or minimal medical intervention/therapy required)
- 3 = Severe: Marked limitation in activity, some assistance usually required; medical intervention/therapy required, hospitalizations possible
- 4 = Life-threatening: Extreme limitation in activity, some assistance usually required; medical intervention/therapy required, hospitalization or hospice care probable
- 5= Death

Assessment of Association

The association assessment categories that will be used for this study are:

- Associated – The event is temporally related to the administration of the study product and no other etiology explains the event.
- Not Associated – The event is temporally independent of the study product and/or the event appears to be explained by another etiology.

The investigator must provide an assessment of association or relationship of AEs to the study product based on:

- Temporal relationship of the event to the administration of study product;

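### The SAP restricts both primary safety endpoints to treatment-related events; the protocol does not, and ARDS during COVID-19 could largely drop out

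*SAP*

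**What the plan says.** **Protocol.** Section 1 and section 5.3 give the same two primary safety endpoints: "Cumulative incidence of serious adverse events categorized separately as either severe infusion reactions and ARDS during the study period" and "Cumulative incidence of grade 3 and 4 adverse events during the study period". Neither mentions relatedness. Section 7 defines an adverse event as one that counts "whether or not considered related to the study product". Section 5.2.1 compares SAEs and grade 3 or higher events between arms by Fisher's exact test, also unfiltered.

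**SAP.** The section on adverse events of study treatment defines the primary safety endpoints as "the cumulative incidence of treatment-related serious adverse events categorized separately as either severe infusion reactions or Acute Respiratory Distress Syndrome (ARDS") and "cumulative incidence of treatment-related grade 3 and 4 adverse events during the study period". The available SAP text neither defines treatment-related nor explains why the condition was added. The same section also plans a comparison of all SAEs and describes the safety analyses as descriptive.

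**The relatedness rule.** Protocol section 7.1 introduces its two categories with "The association assessment categories that will be used for this study are". An event is Associated if "The event is temporally related to the administration of the study product and no other etiology explains the event". It is Not Associated if it is temporally independent of the product and/or "the event appears to be explained by another etiology".

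**The concern.** The two documents define different primary safety endpoints, and the difference bears most on ARDS. Protocol section 8.3 gives two reasons for watching ARDS: it is a consequence of COVID-19, and it may signal ADE. Section 3.2 describes ADE as enhancement of disease in the presence of antibody. An ADE case would therefore arise in someone who has COVID-19, and COVID-19 is a ready alternative explanation for the ARDS. A filter that removes events with another explanation bears hardest on the harm that ARDS is meant to reveal.

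What is at stake is the result the trial would report as its primary safety finding. It would not be the endpoint the protocol promises, and it would rest on a causality judgement the available SAP text leaves undefined. In a masked randomised trial, the all-cause difference between arms needs no such judgement.

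**Working it through.** **1. The definitions side by side**

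| Endpoint | Protocol 1 and 5.3 | SAP |
|---|---|---|
| SAEs: severe infusion reactions, ARDS | all causes | treatment-related only |
| Grade 3 and 4 AEs | all causes | treatment-related only |

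**2. How the association rule acts on ARDS.** The Not Associated category is joined by and/or, so another apparent etiology is enough by itself. Section 8.3 names COVID-19 as a cause of ARDS. ARDS in an infected participant can therefore be classed Not Associated. Section 7.1 also lists biological plausibility among the factors to weigh, so some cases may still be attributed to plasma. Severe infusion reactions would be little affected.

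**3. The protocol's own ARDS figures carry no relatedness filter.** Table 3 in section 8.3 takes 75 per arm, with 20% and 5% symptomatic: 75 × 0.20 = 15, and 75 × 0.05 = 3.75, rounded to 4. At a 40% ARDS rate:

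- Control: 1 − 0.60^15 = 0.9995 (table: >0.999); expected cases 15 × 0.40 = 6.0.
- HCIP: 1 − 0.60^4 = 0.8704 (table: 0.870); expected cases 4 × 0.40 = 1.6 (the text rounds to two).

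The table reproduces with every ARDS case counted.

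**4. The same figures under a relatedness filter.** Let *f* be the share of ARDS cases judged associated, assumed equal in both arms. The documents do not give *f*. Expected cases are 6.0*f* and 1.6*f*; the chance of at least one counted case is 1 − (1 − 0.40*f*)^n, with n = 15 or 4.

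| *f* | Control: expected; chance of ≥1 | HCIP: expected; chance of ≥1 |
|---|---|---|
| 1 | 6.0; >0.999 | 1.6; 0.870 |
| 0.5 | 3.0; 0.965 | 0.8; 0.590 |
| 0.2 | 1.2; 0.714 | 0.32; 0.284 |
| 0.1 | 0.6; 0.458 | 0.16; 0.151 |
| 0 | 0; 0 | 0; 0 |

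**5. The full trial.** With 250 per arm and the symptomatic rates of protocol section 5.1, 250 × 0.13 = 32.5 control cases and 250 × 0.065 = 16.25 HCIP cases. One ARDS rate is applied to both arms, as section 8.3 does.

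- At 3.4%, which section 8.3 reports for all subjects (using it for symptomatic cases is an assumption): 32.5 × 0.034 = 1.105 and 16.25 × 0.034 = 0.5525, total 1.66.
- At the 40% worst case: 32.5 × 0.40 = 13.0 and 16.25 × 0.40 = 6.5, total 19.5.

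The SAP endpoint would count *f* times these totals: none at *f* = 0, 0.83 or 9.75 at *f* = 0.5, and 1.66 or 19.5 at *f* = 1.

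**6. Effect on the contrast.** With equal *f*, the ratio of expected counts is unchanged but the risk difference is multiplied by *f*. In the 40% case the difference is (13.0 − 6.5)/250 = 2.6 percentage points for all causes and 1.3 points at *f* = 0.5.

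These are expected counts, not power. The documents plan no ARDS-only test.

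**The case against.** The mismatch in wording is not in dispute. The case against concerns its consequence.

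- **The share lost is unknown, and the SAP does not say that treatment-related means Associated.** The first part is correct, so the size is given only as a range. On the second, section 7.1 states its categories for the whole study. The protocol's other scale (definite, probable, possible, unlikely; section 8.3) is applied only to deaths. If the SAP meant something else, the term is ambiguous as well as restrictive.
- **The counts are illustrative.** This stands. The 40% rate is the protocol's self-described worst case, and the 3.4% rate is moved to a different denominator.
- **Unfiltered analyses remain.** This stands and limits the harm. The SAP compares all SAEs, shows overall AE and SAE numbers by arm (by organ system where they differ), and gives special attention to ARDS and deaths in the HCIP group. Protocol 5.2.1 compares SAEs and grade 3 or higher events, and section 8.3 has the DSMB review ARDS. But the SAP's all-SAE comparison is pooled, its severity scale has no ARDS level, and it plans no all-cause cumulative incidence of ARDS or of grade 3 and 4 events.
- **Causality is judged under masking, so no differential bias is shown.** Agreed. The loss is of events and absolute difference.
- **The definition of an adverse event is not contradicted by reporting a related subset.** Also agreed. The conflict is between the endpoint definitions; the AE definition shows only that all-cause data will be available.
- **The narrowing may be deliberate.** Possibly, since the SAP cites a list dated after the protocol version. No reason is given in the available text, and the protocol still promises the unrestricted endpoints.

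**Conclusion.** The concern holds. The SAP narrows both primary safety endpoints relative to the protocol. If section 7.1 is the rule applied, ARDS in participants with COVID-19 could largely drop out of the first endpoint. That consequence is conditional on how investigators weigh COVID-19 against biological plausibility, and the documents do not allow the share to be estimated. On the assumptions shown, about 1.7 to 19.5 ARDS cases across both arms would be exposed to that judgement.

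This should be fixed but does not undermine the trial: unfiltered safety analyses survive, and sample size, alpha and efficacy power are untouched.

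**What to change.** Delete the treatment-related condition from both primary safety endpoints in the SAP, so that they match protocol sections 1 and 5.3, and compare all-cause events by randomised arm. Keep the grade 3 or higher comparison of protocol 5.2.1 as the separate analysis it already is. Report investigator-attributed events in a supportive table, naming the section 7.1 rule as the basis. State that the all-cause ARDS difference measures net harm: it mixes prevention of infection with any enhancement of disease and does not isolate ADE.

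The cost is SAP wording only, because adverse events are already collected regardless of cause. Reported event rates will be higher than under the restricted definition. If the sponsor did intend the narrowing, the alternative is to amend the protocol, justify the change and define the term; the primary safety result would then still depend on attribution.

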### **Interim monitoring:**

A multidisciplinary DSMB that will be responsible for the protection of the safety of participants enrolled in the trial. The DSMB will adopt a charter describing its responsibilities and operating characteristics. The DSMB will review the accumulating data on the primary outcome measure (SARS-CoV-2 positivity). The overall event rate (i.e., not separated by treatment arms) will be used by the DSMB to help make recommendations to mitigate risk to not successfully completing trial by providing suggestions about modifying the trial. Tracking overall event rate allows for suggestions to be made without spending alpha by conducting an interim efficacy analysis (with the exception of the planned interim analysis).

There will be two formal reviews of interim efficacy results. The first will occur after 15 COVID-19 (symptoms compatible with infection and/or RT-PCR positive) occur (after about 150 individuals) and the second after 50 percent of the randomized participants have completed 28-day follow-up data collection. Interim analysis will be adjusted for age. Stopping guidelines will be based on O'Brien Fleming boundaries; with two planned interim look (after 15 events, after 50% reach day 28), the Z-values are 3.03 (nominal p-value of 0.0011, spent alpha 0.0011), 2.38 (0.0087, 0.008), and 1.68 (0.464, 0.408) for a one-sided test with Type 1 of 0.05, respectively.

All measures will be evaluated for outliers, and distributional assumptions will be checked to ensure applicability of the statistical procedures.

The DSMB will make recommendations to the principal investigators about continuing, modifying, or stopping the trial. The DSMB will meet periodically to review interim reports and analyses derived from the accumulating data or related findings from sources external to the trial that may be needed to make recommendations to the principal investigators regarding: 1) overall efficacy and benefit/risk ratio, 2) efficacy and benefit/risk ratios within defined subsets of participants, and 3) overall and clinic-specific performance and data quality.

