hypertension, and serious heart conditions (heart failure, coronary artery disease, cardiomyopathies, pulmonary hypertension) [Guan W-j, Liang W-h, Zhao Y, et al. Comorbidity and its impact on 1590 patients with COVID-19 in China: a nationwide analysis. *Eur Respir J* 2020; 55: 2000547, <https://www.cdc.gov/coronavirus/2019-ncov/need-extra-precautions/groups-at-higher-risk.html>].

The primary outcome analysis will be the adjusted comparison of proportions of cumulative incidence of SARS-CoV-2 infection (symptoms compatible with infection and RT-PCR positive) at day 28 comparing the risk-difference and restricted mean survival time between treatment groups with a significance threshold of $p=0.047$ (p -value adjusted for interim analysis) for a one-sided test.

Finally, statistical inference will use a one-sided Type 1 error rate of 0.05 for superiority and 95% confidence intervals (note: interim analyses are based upon O’Brian-Flemming spending function see below under section 8.3 Halting Criteria for Study).

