8.3. Halting Criteria for the Study

The study enrollment and dosing will be stopped and an ad hoc review will be performed if any of the specific following events occur or, if in the judgment of the study physician, subject safety is at risk of being compromised:

- I. Unexpected death of a dosed subject in relation to infusion
- II. Occurrence of a life-threatening allergic/hypersensitivity reaction (anaphylaxis), manifested by bronchospasm with or without urticaria or angioedema requiring hemodynamic support with pressor medications or mechanical ventilation.
- III. One subject with an unexpected SAE associated with study product.
- IV. Two subjects with a Grade 3 or higher toxicity for the same parameter associated with study product.
- V. An overall pattern of symptomatic, clinical, or laboratory events that the medical monitor, ISM, or SMC consider associated with study product and that may appear minor in terms of individual events but that collectively may represent a serious potential concern for safety.
- VI. Any other event(s) which is considered to be a serious adverse event in the good clinical judgment of the responsible physician. This will be appropriately documented.

Interim Analyses for efficacy: There will be two formal review of interim results. The first will occur after 15 infections which is expected to occur near 150 participants reaching day 28 and the second after 50% of the total recruitment (n=500) has been achieved and these individuals followed to at least day 28. Interim analyses will only be adjusted for age. Stopping guidelines will be based on O’Brien-Flemming boundary. The interim analysis Z-value boundary of 3.03 (nominal p-value of 0.0011, spent alpha 0.0011), 2.38 (0.0087, 0.008), and 1.68 (0.464, 0.408) for a one-sided test with Type 1 of 0.05.

Special considerations for death:

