## **Power and Sample Size**

We hypothesize that outpatient adults with recent exposure to COVID-19 who receive HCIP will have a lower incidence of developing a SARS-CoV-2 infection with COVID-19 when compared with similar adults receiving control plasma. A sample size of 500 individuals with a high risk exposure within 96 hours of enrollment with a 1:1 allocation ratio to each treatment group will have 80% power to detect a 50% reduction in cumulative incidence by 28 days. This is with a one-sided type 1 error of 5% as we are solely interested in superiority. We assumed that the probability of incident COVID-19 cases is between 0.10 and 0.20 in the control population. We explored several different scenarios with an exponential model to identify the lambda parameter and the package 'powerSurvEpi' for the R statistical software was then used to calculate the sample sizes for these scenarios (See Table1). We assumed that the cumulative incidence of symptomatic disease in SARS-CoV-2 exposed individuals randomized to control plasma to be 0.13X by day 28 and 0.065 (50% reduction in risk) by day 28 among those randomized to HCIP. We therefore estimated 488 participants (244 in each arm). It is

---

\*with surge of infections in December 2020 and hospitals becoming more full, these two were put into the clinical events scale as hospitalization equivalents

anticipated that very few of these subjects will be randomized and not start study plasma infusion (and so be excluded from the primary analysis). Furthermore, it is anticipated that there will be low loss to follow-up prior to development of disease or 28 days (and so have missing data for the primary endpoint). Therefore, we have extended the total sample size to 500 participants. For all analyses, we will use a modified intention-to-treat analyses, which excludes randomized subjects who do not initiate an infusion of the study plasma.

Table 1: Total sample size by the incident proportion of COVID-19 among controls and by percent risk reduction

Proportion of Incident COVID-19 cases at day 28 among controls	50% Risk Reduction	75% Risk Reduction
0.10	648	199
0.13	488	150
0.15	415	129
0.20	298	94

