Our analysis will be a time to event analysis examining the effect of anti-SARS-CoV-2 plasma. We will estimate the survival function for each treatment arm in order to estimate the risk difference over time as well as the restricted mean survival time which is the area under the survival function and provides the expected mean time to infection up to time  $t^2$ . Our approach will be to estimate the cumulative incidence using the doubly robust estimator based upon targeted minimum loss (TMLE) based estimator as described by Diaz et al (2019). By adjusting for baseline covariates that are related to the outcome, we increase precision. This TMLE based approach was shown to increase precision by around 10% to 20% over an inverse probability weighted or augmented inverse probability weighted estimator [Diaz 2019]. As stated above, we will use a hybrid approach of adjusting for pre-specified variables (age) and an algorithmic approach to identify additional variables related to the outcome. Specifically, a random survival forest will be used to identify variables that are related to the outcome in order to increase precision. We will use a random survival forest blinded to the treatment arm allocation and *not* including an indicator variable for treatment (pre-randomization variables to be considered are listed above).

The primary outcome analysis will be the adjusted comparison of proportions of cumulative incidence of SARS-CoV-2 infection (as indicated by RT-PCR positive) at day 28 comparing the risk-difference and restricted mean survival time between treatment groups with confidence intervals and using a significance threshold of  $p=0.047$  (p-value adjusted for interim analysis) for a one-sided test. This will be repeated for analysis of the cumulative incidence of SARS-CoV-2 symptomatic disease as defined as having a confirmed SARS-CoV-2 positive test and at least one symptom including new/incident: fever, cough, sore throat, malaise, headache, muscle pain, nausea, vomiting, loss of taste, loss of smell, shortness of breath, or dyspnea as per the FDA recommendations in Appendix A within "COVID-19: Developing Drugs and Biological Products for Treatment or Prevention: Guidance for

Industry [<https://www.fda.gov/media/137926/download>]. Therefore, we will be assessing both the effect of convalescent plasma on overall infection including asymptomatic disease and its effect on symptomatic disease.

Additional sensitivity analysis include:

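### The final-look nominal p (0.464) and spent alpha (0.408) are printed ten times too large in three places, and the final success criterion appears in two forms that agree only through rounding

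*SAP*

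**What the plan says.** The same boundary figures appear in Protocol 8.3 (Halting Criteria), SAP Statistical Principles and SAP Interim monitoring. Each entry is a Z value followed by a nominal p and a spent alpha.

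- First look, after 15 infections: "The interim analysis Z-value boundary of 3.03 (nominal p-value of 0.0011, spent alpha 0.0011" in Protocol 8.3.
- Second look (50%) and final look: "2.38 (0.0087, 0.008), and 1.68 (0.464, 0.408) for a one-sided test with Type 1 of 0.05" in SAP Interim monitoring. The other two places carry the same figures.

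The overall error is one-sided 5%. The SAP's Power and Sample Size section says "This is with a one-sided type 1 error of 5% as we are solely interested in superiority".

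The final threshold is stated again in Protocol 5.2 and in the SAP's Primary Analysis. Both compare the risk difference and "restricted mean survival time between treatment groups with a significance threshold of" p = 0.047 (Protocol wording), described as adjusted for the interim analyses and one-sided.

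On the type of rule, SAP Interim monitoring refers to "Fleming boundaries; with two planned interim look (after 15 events, after 50% reach day 28", whereas Protocol 5.2 calls it an O'Brien-"Flemming spending function see below under section 8.3 Halting Criteria for Study".

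**The concern.** A nominal p of 0.464 cannot belong to Z = 1.68, and one look cannot spend 0.408 out of a total of 0.05. These figures sit beside the efficacy boundaries. The SAP says the DSMB will adopt a charter, and it lists exceeding the planned boundaries as a reason to stop, so the figures are likely to be copied.

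The plan also gives the final criterion as Z = 1.68 and as p = 0.047. If both are read as exact, a final p between 0.0465 and 0.047 passes under one statement and fails under the other. A pre-specified success rule should have one value.

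**Working it through.** **Inputs.** Z values 3.03, 2.38 and 1.68 with their printed p values and spends (Protocol 8.3; SAP Statistical Principles and Interim monitoring). Overall one-sided alpha 0.05. Final threshold 0.047 (Protocol 5.2; SAP Primary Analysis). Planning rates 13% and 6.5% (Protocol 5.1) with 250 per arm. The documents state no information fraction at the first look, so two are assumed:

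- 150/500 = 0.30, from the participants expected by then.
- 15/48.75 = 0.308, where 48.75 = 250 × (0.13 + 0.065) expected events.

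The second look is taken at 0.5 and the final at 1.

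**1. Nominal p from the printed Z, one-sided: p = 1 − Φ(Z)**

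| Look | Printed Z | Printed p | Recomputed p |
|---|---|---|---|
| 1 | 3.03 | 0.0011 | 0.0012 |
| 2 | 2.38 | 0.0087 | 0.0087 |
| Final | 1.68 | 0.464 | 0.0465 |

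The second look reproduces. The final one does not: p = 0.464 would need Z = 0.09, and the two-sided p for 1.68 is 0.093, so sidedness does not explain it.

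**2. Spent alpha.** The printed spends give 0.0011 + 0.008 + 0.408 = 0.417, against a total of 0.05. Numerical integration of the first-crossing probabilities for the printed Z values, with the first look at 0.308, gives 0.0012 + 0.0079 + 0.0409 = 0.0500.

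**3. Where the printed digits come from.** The classic O'Brien-Fleming boundary sets Z = C/√t, with C chosen so that the overall one-sided alpha is 0.05.

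| First-look information | Z | Nominal p | Spend per look |
|---|---|---|---|
| 0.308 | 3.030 / 2.377 / 1.6807 | 0.0012 / 0.0087 / 0.0464 | 0.0012 / 0.0080 / 0.0408 |
| 0.30 | 3.068 / 2.376 / 1.6804 | 0.0011 / 0.0087 / 0.0464 | 0.0011 / 0.0081 / 0.0409 |

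The first row gives all three printed Z values and the digits 464 and 408 with the decimal point one place to the left. Replacing only the slipped spend gives 0.0011 + 0.008 + 0.0408 = 0.0499, or 0.050 to three decimals.

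**4. The 0.047 threshold.** p = 0.047 is Z = 1.6747. With interim bounds 3.03 and 2.38:

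- final Z = 1.68: overall alpha 0.0500
- final p = 0.047 exactly: overall alpha 0.0505

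Under the planning effect, the drift is 0.065/√((0.13 × 0.87 + 0.065 × 0.935)/250) = 2.465 (unadjusted two-proportion approximation). The chance of success over all three looks is 0.7894 with 0.047 and 0.7879 with 1.68, a difference of 0.0015.

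**5. First look.** Any Z that rounds to 3.03 (3.025 to 3.035) has p between 0.00120 and 0.00124, so 0.0011 cannot come from it. The p fits information 0.30 (Z about 3.07), and the Z fits about 0.308.

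**The case against.** The strongest reply is that nothing operational depends on the slip. The Z values are printed beside the p values, they hold overall alpha at 0.0500, and no one would treat p < 0.464 as success in a design stated as one-sided 5%. That stands, and it is why the point is minor. It does not make the printed figures right. PDF extraction is an unlikely cause, since the same figures appear in two documents and three places while the neighbouring entries are intact.

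Four stronger readings are tempting, and the documents do not support them:

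- **That the trial's type I error is inflated to 0.4 or more.** That would require 0.464 to be the operative rule. The Z of 1.68, the stated total of 0.05 and the 0.047 threshold all contradict it.
- **That 0.047 is an arithmetic error against Z = 1.68.** At printed precision the two are compatible: Z = 1.675 rounds to 1.68 and has p 0.04697; Z = 1.678 has p 0.0467. What remains is that 0.047 is not a rounding of 0.0464 and, taken as exact, gives 0.0505.
- **That the term spending function in Protocol 5.2 means the printed bounds are wrong.** That passage names no formula and sends the reader to section 8.3, where explicit Z values are printed as a boundary. Only the wording needs aligning.
- **That the 95% confidence intervals in Protocol 5.2 conflict with the one-sided test.** The text does not say whether they are one- or two-sided, so this is at most a request for clarification.

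**Conclusion.** Wrong as written, minor. The final-look p and spend are each tenfold too large in three places: 0.464 and 0.408 should be 0.0464 and 0.0408. This rests only on the normal distribution and the stated total of 0.05 for the size of the slip, and on the classic O'Brien-Fleming form for the fourth decimal.

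The final criterion should also be made single. If 0.047 is read as exact, the difference from Z = 1.68 is 0.0005 in overall alpha and about 0.15 percentage points of power. The power figure assumes the 13% and 6.5% planning rates, an unadjusted comparison and a first look at information 0.308.

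Two footnotes: the first-look p should be 0.0012 if Z = 3.03 is kept, and the label in Protocol 5.2 should match section 8.3. The printed Z values control the overall one-sided error at 0.050, so the error rate is not at risk.

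**What to change.** 1. In Protocol 8.3, SAP Statistical Principles and SAP Interim monitoring, print the final look as 1.68 (0.0464, 0.0408). Say that the spends are per look and that 0.05 is the total over the three looks.
2. State one final success criterion there and in Protocol 5.2 and SAP Primary Analysis, to enough decimals that Z and p agree (1.6807 with 0.0464; a rounded 1.68 gives 0.0465). If this replaces 0.047, record it as a very slight tightening of the success criterion rather than as a typographical correction.
3. Make the first-look pair consistent and state the information fraction: 3.03 with 0.0012 at 0.308, or 3.07 with 0.0011 at 0.30.
4. In Protocol 5.2, replace the spending-function wording with the boundary printed in section 8.3. If a spending function was meant, name it and recompute the bounds.

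The cost is low: figures and wording in five places. The sample size and the second-look bound do not change, the final bound stays at 1.68 to two decimals, and the first-look Z moves only if 3.07 is chosen. Only the second alternative in item 4 would require new boundaries.
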